**Sponsor activities**

Philips, as the sponsor, will be responsible for:

- Internal Ethics approval
- Providing Principal Investigator
- Study Design
- Monitoring
- Data storage
- Data integrity check
- Data analysis
- Report

**Supplier (CRO activities):**

- Selection of rooms for data collection
- Selection of psychometrists
- IRB approval
- Recruitment of participants
- Data collection

## 6.5 Monitoring plan

In accordance with 21 CFR 312.56, the clinical monitor will periodically inspect all CRFs, study documents and research facilities associated with this study at mutually convenient times during and after completion of the study. As required by FDA regulations (Responsibilities of Sponsors and Investigators), the monitoring visits provide the Sponsor with the opportunity to evaluate the progress of the study; verify the accuracy and completeness of CRFs; ensure that all protocol requirements, applicable FDA regulations, and investigator’s obligations are being fulfilled; and resolve any inconsistencies in the study records. This includes inspection of all documents and records that are required to be maintained by the investigator.. The names and identities of all research subjects will be kept in strict confidence and will not appear on CRFs or other records provided to or retained by the Sponsor. The regulations also require the investigator to allow authorized representatives of the FDA to inspect and make copies of the same records. The names and identities of the subjects need not be divulged to the Sponsor; however, the records must nevertheless be inspected. This can be accomplished by blacking out the subject’s name and replacing the name with the subject’s study ID number. If these requirements are in conflict with local regulatory restrictions or institutional requirements, the investigator must inform the Sponsor of these restrictions prior to initiation of the study.

See the Monitoring Plan for a description of how monitoring of the conduct and progress of the clinical study will be conducted. Monitoring of the study will be conducted by Philips according to the monitoring plan (CT18\_Monitoring\_Plan).

## 7 STATISTICAL CONSIDERATIONS

**Statistical design, analyses and power considerations**

Below we describe the planned analyses for each aim and hypothesis. The tests are scored by two raters (with 30% overlap) and inter-rater agreement is assessed prior to proceeding with the following analyses. All correlations mentioned below are Pearson correlations. Retest correlations are corrected for the variability of the normative sample (Allen & Yen, 2002; Magnusson, 1967). Correlation between paper and pencil measures are corrected for measurement error (Padilla & Veprinsky, 2012). In our power analyses we assume an alpha of .05.

Title: Clinical Investigation Plan		Author: [name]		Company Restricted	
DocID: ICBE-2-28674	Version: 2.0	Date: 2019-02-18	Status: Approved	Page: 25 of 35	
IRBMANAGER PILOT – QI PROJECT					

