The ISC production equivalent that will be used for administering O Cancellation Test, Category Fluency Test, RAVLT, COWAT and Star Cancellation has the exact same patient interface as the end-product. The digital tests will be provided to the participants on an iPad Pro tablet (Apple). It has a screen size of 12.9-inches with a screen resolution of 2732x2048. This is the exact same tablet as required for use of the final ISC product.

Participants will use the Apple pencil for the iPad Pro tablet to perform the digital tests (see Figure 1). The tablet will present instructions for each test to participants via both written text and audio recordings. A researcher will observe in order to ensure that the participant understands and follows the instructions (see Figure 2). The iPad Pro tablet, Apple pencil and the regular laptop, which may be used by the researcher to take notes, are all CE marked devices.

Figure 1. iPad pro and Apple pencil used by the participant

Figure 2. Regular laptop used by researcher

The ISC production equivalent and ISC product (verified for data collection, SW version 1.0.0) are only utilized to collect data. The scoring algorithms for the ROCFT and the Clock Drawing Test have either not yet been implemented or the output of those that have been implemented will not be considered relevant. The data collected with the device during the clinical investigation will be used to assess the equivalence of outputs from automatic scoring by the algorithms to traditional manual scoring. Only when the output of the algorithms have high agreement with manual scores of the respective test, the algorithms will be integrated into the final ISC product.

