### 3 JUSTIFICATION

While the ISC product may be used in a variety of situations the most likely is within a neurology office. The use-case for ISC is that the raw data are collected via the ipad under the supervision of an assistant.

Title: Clinical Investigation Plan		Author: [name]		Company Restricted	
DocID: ICBE-2-28674	Version: 2.0	Date: 2019-02-18	Status: Approved	Page: 17 of 35	
IRBMANAGER PILOT – QI PROJECT					

Subsequently, various algorithms are applied to score the individual tests. These scores are then fed into a cognitive model, resulting in easy-to-interpret cognitive domain scores. The domain scores are norm referenced by age, and optionally by gender, education, and ethnicity. The output of ISC is used by the neurologist to help him/her arrive at his/her diagnosis or for creating an optimal therapy plan. In the case of recurring visits the cognitive domain scores give the neurologist (or HCP) metrics to objectively assess change over time.

A USA neurologist will on average send 13% of his patients for a full neuropsychological assessment while in an ideal world he/she would like to send 36% (The MarkeTech Group, 2018). A common reason for not referring for a full assessment is the waiting time of 3-6 months (The MarkeTech Group, 2018). There is a clear unmet need for a solution that gives more information than a simple screener tool but within an actionable time-window, preferably during the patient visit. For the majority of patients, ISC doesn't replace the full neuropsychological assessment but instead helps triage patients so that people that need a full assessment can be quickly identified and fast tracked.

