### 6.2 Investigational device(s) and comparator(s)

The investigational devices are the ISC product and the ISC product equivalent. The comparators are the paper-pencil tests included in the study.

Manual scores of the digital ROCFT and Clock Drawing Tests will be compared to the algorithm scores. Scoring algorithms for the ROCFT and the Clock Drawing Test are applied post-data collection. The scores estimated by the algorithms will be compared with manual scoring by a sample of well-trained raters (n = 6; aim 2). The algorithms have been developed by Philips Research and after positive comparison to the manual scores will be part of future releases of the ISC product. By comparing the manual and algorithm scoring, we can investigate the agreement between the two for the tests on the platform. This will be done by computing the relative inter-rater agreement (also known as inter-rater reliability) between the algorithm and expert raters. Relative inter-rater agreement implies that the algorithm ranks examinees the same as expert raters (n = 6).

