**Aim 3. Estimate regression-based norms and reliable change indices**

Title: Clinical Investigation Plan		Author: [name]		Company Restricted
DocID: ICBE-2-28674	Version: 2.0	Date: 2019-02-18	Status: Approved	Page: 26 of 35
IRBMANAGER PILOT – QI PROJECT				

The data collected can be used to establish regression-based norms. 250 (up to 300) participants (group A&C, phase 1 and group E) will be included in the norm group. These norms can be used for the IntelliSpace Cognition tool and may be updated at a later point in time.

Reference scores (for age, educational level, gender, and ethnicity) will be generated using linear regression techniques. We will additionally estimate regression based reliable change indices.

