**Sample size**

The study will include a total of  $N = 400$  (up to  $N=450$ ) healthy individuals, without accounting for drop-out (see Figure 1 for the design); The tests will be scored by two well-trained raters. Moreover, to compute the inter-rater agreement between scoring algorithms and manual scoring we need six additional well-trained raters.

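### Digital ROCFT and Clock Drawing: the scoring rule implies that norms, change indices, loadings and retest figures come from rater scores, while the product would use algorithm scores if they pass Aim 2

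*Combined protocol and SAP*

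**What the plan says.** **Scoring rule.** Section 7 opens with a rule for all the aims: "The tests are scored by two raters (with 30% overlap) and inter-rater agreement is assessed prior to proceeding with the following analyses". The Executive Summary (Investigation procedures) and section 7 (Sample size) also have two raters score the tests. Aim 3 and Aim 4 name the groups whose digital data are used but do not say who or what scored the drawings.

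**Algorithms in the study.** Section 6.2 says "Scoring algorithms for the ROCFT and the Clock Drawing Test are applied post-data collection" and describes a comparison with six raters. Section 6.1 and Aim 2 set that comparison on 100 randomly drawn sets of drawings. The Sample size paragraph adds that "to compute the inter-rater agreement between scoring algorithms and manual scoring we need six additional well-trained raters". No other use of algorithm scores is stated.

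**Algorithms in the product.** Section 3 describes the intended use: "Subsequently, various algorithms are applied to score the individual tests. These scores are then fed into a cognitive model", after which the domain scores are norm-referenced. Section 2.3 makes this conditional: "Only when the output of the algorithms have high agreement with manual scores of the respective test, the algorithms will be integrated into" the final product.

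**Norms.** Under Aim 3, "These norms can be used for the IntelliSpace Cognition tool and may be updated at a later point in time". Section 8 (Data retention) says that the study's digital data will form the device's norm data set.

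**The concern.** For these two tests, the score that is normed, retested and modelled under the plan's rule is not the score that the product would report. The only planned link between the two is Aim 2, and section 6.2 defines agreement there as relative, meaning that algorithm and raters rank examinees alike. Two scores can rank people alike and still differ in mean or spread.

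At stake are norm scores and change indices estimated on one score and applied to another, with retest reliability and loadings never estimated for the algorithm score. The plan limits the digital-paper difference to 0.3 sd (Hypothesis A) but sets no such limit between algorithm and rater.

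**Working it through.** **1. Which score goes where (digital ROCFT and Clock Drawing)**

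| Analysis | Data | Score implied by the plan | Score in the product if Aim 2 passes |
|---|---|---|---|
| Aim 3 norms | A and C phase 1, E | rater | algorithm |
| Aim 3 change indices | C | rater | algorithm |
| Aim 4 loadings | A and C phase 1, E | rater | algorithm |
| Retest, digital | C, both phases | rater | algorithm |
| Aim 2 agreement | 100 drawing sets | both, by correlation | n/a |

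**2. What Aim 2 can detect**

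For b > 0, corr(a + bX, Y) = corr(X, Y), so an offset a or a rescaling b leaves every Aim 2 correlation unchanged. The plan's power of at least 80% for Aim 2 comes from a simulation in a technical note whose inputs are not in the documents, so it cannot be reproduced. A separate simulation of the described test used 6 raters, 100 drawings, Fisher z, bounds of ±.1 around the rater correlation and alpha .05. It assumed that inter-rater and algorithm-rater correlations were equal, at .80 to .95. The pass rate was about 100% with no offset, and also about 100% with offsets of 0.3, 0.5 and 1.0 SD. At a true correlation of .90, the alternative criterion of r > .8 was also met in about 100% of runs at every offset.

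**3. Effect of an offset or scale difference on a single-test norm score**

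Assume normal scores and manual-score norms. Let d be the algorithm offset in SD and k the ratio of algorithm SD to rater SD. The share of healthy people below a cut c is Φ(c − d) for an offset and Φ(c/k) for a scale difference. The offsets, ratios and cuts are assumptions.

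- No difference, c = -1.5: Φ(-1.5) = 6.7%
- d = -0.2: Φ(-1.3) = 9.7%
- d = -0.3: Φ(-1.2) = 11.5%
- d = -0.5: Φ(-1.0) = 15.9%
- d = +0.3: Φ(-1.8) = 3.6%, so low scorers would be missed
- k = 1.2: Φ(-1.25) = 10.6%; k = 0.8: Φ(-1.875) = 3.0%
- At c = -2, d = -0.3: from Φ(-2) = 2.3% to Φ(-1.7) = 4.5%

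**4. What these scenarios do not change**

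A constant offset or a rescaling leaves retest correlations and standardised loadings as they are. In a regression-based change index with slope b, an offset d present at both visits leaves d(1 − b). With b = .7 (the plan's expected retest level, assuming equal SDs), 0.3 × (1 − .7) = 0.09 SD, so most of it cancels. Retest correlations and loadings could differ for another reason: at r = .8 the two scores share .8² = 64% of their variance, and the other 36% includes algorithm-specific as well as rater error. The documents do not allow that effect to be sized.

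**5. What the stored drawings would give**

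Digital participants: A 100 + B 100 + C 50 + E 100 = 350, or up to 400 with the 50 aged 50-54.

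- 95% interval for an observed r = .85 by Fisher z: .78 to .90 at n = 100, and .82 to .88 at n = 350.
- Mean shift detectable with 80% power (two-sided .05, one rater score per drawing, equal SDs): (1.960 + 0.842) × √(2(1 − r)) / √n. At n = 100 this is 0.18 SD for r = .8 and 0.13 SD for r = .9. At n = 350 it is 2.802 × 0.632 / 18.71 = 0.09 SD and 2.802 × 0.447 / 18.71 = 0.07 SD.

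**The case against.** The strongest reply is that the plan never says the norms and loadings for these tests rest on rater scores. That is inferred from a general rule, and nothing forbids scoring every stored drawing by algorithm. The remark in section 2.3 that "the output of those that have been implemented will not be considered relevant" concerns output while the software is only collecting data, and does not settle which score feeds the norms. This stands, and it is why the point says that the plan implies rater scores. But the rule is stated as covering the analyses that follow, and no aim departs from it, so an analyst following the plan would use rater scores.

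Four stronger readings are tempting, and the documents do not support them.

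- *The marketed device has no valid norms.* Only two of ten tests are affected, algorithm use depends on passing Aim 2, and the norms may be updated later. If an algorithm fails, the manual-score norms apply.
- *The digital-paper comparison is defective.* Scoring both versions by hand isolates administration mode and is the right primary analysis for Hypothesis A.
- *The retest and loading figures are shown to be wrong for the algorithm score.* They are simply not estimated for it.
- *The percentages are error rates of the device.* They describe one test under assumed offsets, whereas the product norm-references domain scores, in which one test carries only part of the weight.

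It can also be said that a check of mean and spread in Aim 2 would largely carry the manual norms over. That is fair for the norms, but the plan has no such check, and it would not supply the algorithm's own retest correlation or loadings.

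**Conclusion.** The point holds for the digital ROCFT and Clock Drawing Test. Followed as written, the plan yields norms, change indices, loadings and a retest correlation for rater scores, and none for the algorithm scores that the product would use after a successful Aim 2. A correlation-only Aim 2 cannot reveal a mean or scale difference.

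The size is unknown because the documents give no offset. Under normality, an assumed 0.3 SD downward offset moves the share below z = -1.5 on the single test from 6.7% to 11.5%, and an upward offset of that size moves it to 3.6%. The effect on a domain score is smaller, in proportion to the test's weight, which the documents do not give. Because the remedy uses data already held, the change should be made even if the true offset proves small.

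**What to change.** Before results are seen, state in section 7 which score is used for the digital ROCFT and Clock Drawing Test in each aim, and add the following.

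1. Run the locked algorithms on all stored digital drawings: A phase 1, B phase 2, C both phases, and E.
2. For each algorithm that passes Aim 2, derive the Aim 3 norms and change indices, the Aim 4 loadings and the group C retest correlation from the algorithm score. If it fails, keep the manual-score analyses.
3. Keep manual scoring of both versions as the primary Hypothesis A comparison, and add algorithm-scored digital against manually scored paper as a supplementary one.
4. Report the algorithm-manual mean difference, SD ratio and correlation on all digital participants (350, up to 400), alongside the six-rater sample of 100.

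The cost is protocol wording, some computing and a few more tables. The drawings are stored and their manual scores already planned, so no new participants, raters or sessions are needed. Applying locked algorithms also respects the Executive Summary's commitment that these data are not used for training.

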**Aim 1 comparison of psychometrics.**

Hypothesis A: Digital and paper-pencil test scores are comparable.

For each test, we will first compute age-only referenced scores for digital and paper-pencil version separately. Referenced scores are computed based on the regression based norms (procedure described below under aim 3) and are represented as z-scores indicating a participant's deviation from what would be expected based on the norm sample for a participant with identical demographic characteristics. We then compute the correlation between digital and paper-pencil referenced scores within participants in group A and B (which are the groups in which participants completed both digital and paper-pencil versions of the tests), which needs to be  $r > .6$  to be considered comparable. Our planned sample size allows us to detect a correlation of  $r > .2$  with 80% power. We also perform an equivalence test for each test, comparing the distribution of digital normed scores with paper-pencil normed scores, using a two-one-sided-t-test approach (TOST; Schuirmann, 1987), with equivalence bounds of  $\pm .3$  sd, which we have 99% power to detect. Our planned sample size would allow us to detect equivalence with bounds of at least  $\pm .21$  with 80% power.

Hypothesis B: Test-retest reliability is comparable.

Test-retest reliability will be tested by examining for each test the correlation between the digital tests in phase 1 and phase 2 (group C) and comparing this to the correlation between the paper-pencil tests in phase 1 and phase 2 (group D). High test-retest correlations are expected ( $r > 0.7$ ), except for the ROCFT copy condition, since the scores of this condition generally show a moderate ceiling effect. The planned sample size for group C and group D each yield 80% power to detect  $r > .37$ .

Hypothesis C: Construct validity is comparable.

Construct validity will be investigated by means of two confirmatory factor analyses (CFA), one for each group (digital vs. paper-pencil). We expect to see that the factor structure that fits the paper-pencil data (phase 1, group B & D) well, will also fit the digital data (phase 1, group A & C) well. Assuming that at most two variables per test are included in the CFA, the subject-to-variable ratio is near 10:1 for each CFA.

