The ISC cognitive model is based on mappings between cognitive domains and established outcome measures from well known paper-pencil tests which have many years of validation. It is vital for the validity of the digital tests, the cognitive model and their subsequent use in clinical practice that the comparability between the digital tests on the ISC platform and the corresponding paper-pencil tests is shown. This study aims at investigating the comparability of the relevant digital and paper-pencil cognitive tests, establishing the psychometric properties of the digital cognitive tests and collecting normative data for the digital tests so that the digital tests and the cognitive model can be used in clinical practice. Normative data is data from a reference population that establishes a baseline distribution for a score or measurement, and against which other scores or measurements can be compared. For this objective, data subjects are informed on the data we collect and the possible re-use of this data, including by 3rd parties.

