### Primary hypotheses

The following primary hypotheses will be tested in the study:

Aim 1.

- A. Digital and paper-pencil normed test scores are comparable. We consider the two versions of a test comparable when the digital normed score is on average within .3 sd of the paper normed score and the two normed scores correlate at least .6.
- B. Test-retest reliability of the digital tests is comparable to test-retest reliability of the paper-pencil tests. We consider the reliability to be comparable when we observe no significant difference in a z-test between the digital and the paper-pencil test-retest correlations.

Title: Clinical Investigation Plan		Author: [name]		Company Restricted	
DocID: ICBE-2-28674	Version: 2.0	Date: 2019-02-18	Status: Approved	Page: 20 of 35	
IRBMANAGER PILOT – QI PROJECT					

C. Construct validity of the digital tests is comparable to the construct validity of the paper-pencil tests. We consider construct validity to be comparable when confirmatory factor analysis yields the same factor structure for digital and paper-pencil tests.

Aim 2.

D. The score(s) provided by the ROCFT and Clock Drawing Test scoring algorithms on ISC are correlated highly (> .8) to the score provided by manual scoring for the same drawings.

Aims 3 & 4 have no accompanying hypotheses.

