**Figure 1. Schematic overview of study design.**

Title: Clinical Investigation Plan		Author: [name]		Company Restricted	
DocID: ICBE-2-28674	Version: 2.0	Date: 2019-02-18	Status: Approved	Page: 21 of 35	
IRBMANAGER PILOT – QI PROJECT					

Group	A	B	C	D	E
n	100	100	50	50	100-150
Phase 1 tests	Digital	Paper-pencil	Digital	Paper-pencil	Digital
Phase 2 tests	Paper-pencil	Digital	Digital	Paper-pencil	

All participants of Group A-D in phase 1 will be invited to participate in two assessments that will take place with a time interval of four-five weeks between the two phases to minimize retest effects. Participants will be randomly assigned with minimization for demographic variables (to make sure that the groups do not differ in terms of gender, age, education level, and ethnicity) to one of the following groups:

- Group A ( $n=100$ ) completes digital tests in phase 1 and paper-pencil tests in phase 2,
- Group B ( $n=100$ ) completes paper-pencil tests in phase 1 and digital tests in phase 2,
- Group C ( $n=50$ ) completes digital tests in both phases,
- Group D ( $n=50$ ) completes paper-pencil tests in both phases,
- Group E ( $n=100-150$ ) only completes digital tests in one phase (50% of group E will be enrolled in phase 1 and the other 50% of group E will be enrolled in phase 2).

The data of group A and B are used to compare score distributions within-subjects

The data from groups A-D (phase 1) are used to compare score distributions between-subjects (aim 1).

The data of group C and D are used to assess and compare test-retest reliability (aim 1) and assess reliable change indices (aim 3).

The data of group A (phase 1), group C (phase 1) and group E are used to estimate regression based norms for the digital tests (aim 3), as well as to estimate factor loadings for the structural equation model (aim 4).

The data of group A (phase 1), group B (phase 1), group C (phase 1) and group D (phase 1) are used to compare construct validity (aim 1).

Participants will be randomized with minimization for demographic variables (gender, age, education level, ethnicity).

The purpose of adding the 100-150 participants in Group E is to increase the sample size of participants who completed the digital tests for the first time for the norm data to 250-300.

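### Hypothesis A does not say which norm the paper scores are referenced to, and if each format gets its own norm the ±.3 SD equivalence test cannot see a constant format shift

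*Combined protocol and SAP*

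**What the plan says.** Section 5 (Primary hypotheses, Aim 1 A) sets two conditions for comparability. The first concerns the mean: "the digital normed score is on average within .3 sd of the paper normed score". The second is a correlation of .6 or higher between the formats.

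Section 7 (Aim 1, Hypothesis A) says how the scores are made: "For each test, we will first compute age-only referenced scores for digital and paper-pencil version separately". They come from the Aim 3 regression procedure and are z-scores expressing "deviation from what would be expected based on the norm sample for a participant with identical demographic characteristics". The correlation is taken within groups A and B. The TOST uses bounds of ±.3 sd, with 99% power claimed. The plan adds: "Our planned sample size would allow us to detect equivalence with bounds of at least" ±.21 with 80% power.

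On the source of the norms, section 7 (Aim 3) says "250 (up to 300) participants (group A&C, phase 1 and group E) will be included in the norm group", and section 6.1 gives their purpose: "group E are used to estimate regression based norms for the digital tests (aim 3"). No section names a norm sample or a published norm for the paper tests, or says that the digital norm is applied to paper scores.

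Section 6.1 also mentions a second comparison: "The data from groups A-D (phase 1) are used to compare score distributions between-subjects (aim 1"). Section 7 gives it no scale, method or pass criterion.

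**The concern.** The mean criterion is half of the definition of comparability, and it compares a digital normed score with a paper normed score. The second cannot be computed from the plan as written, and the missing choice decides what the TOST measures.

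If each format has its own norm, both sets of z-scores are centred and scaled on that format before they are compared. A tablet version that is uniformly harder or easier would then look the same as one that is not. The correlation criterion does not help, because a constant shift leaves a correlation unchanged. Hypotheses B and C concern retest correlations and factor structure, not mean level.

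Section 3 regards it as vital "that the comparability between the digital tests on the ISC platform and the corresponding paper-pencil tests is shown", and section 5 rests product claim 3 (psychometrics similar to paper) on Aim 1.

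**Working it through.** **1. The plan's own figures.** Inputs: 200 pairs (A 100 + B 100, counts after dropout, section 6.1); alpha .05, applied to each one-sided test; true difference 0. With the bound in SD of the difference, power = 2Φ(bound × √200 − 1.645) − 1.
- ±.3: .3 × 14.142 − 1.645 = 2.598, power 99.1% (plan: 99%).
- ±.21: .21 × 14.142 − 1.645 = 1.325, power 81.5% (plan: 80%).

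Both figures reproduce. If the bound is instead in norm SD, the SD of the difference is √(2(1 − r)), that is .894, .775 and .632 at r = .6, .7 and .8. Dividing the bound by it gives 99.8%, 100% and 100% at ±.3, and 90.6%, 97.1% and 99.8% at ±.21. The stated figures therefore fit SD-of-difference units, or norm SD at r = .5, which is below the plan's own .6. The plan does not say which unit it means.

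**2. Format-specific norms: algebra.** The digital score is z_D = (D − α_D − β_D × age)/s_D, with α_D, β_D and s_D from a regression on digital data. Add a constant δ to every digital score. The fitted α_D rises by exactly δ, while β_D and s_D do not change, so z_D is unchanged. The mean of z_D − z_P, its SD and its correlation are then the same for any δ. This does not depend on the age slope or on r. A scale difference between formats is likewise absorbed by s_D and s_P.

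**3. One norm for both formats.** z_D − z_P = (D − α − β × age)/s − (P − α − β × age)/s = (D − P)/s. The age term cancels and the shift stays.

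**4. Simulation.** Groups A-E of 100, 100, 50, 50 and 100; ages 55-80; linear age effect, r and shift assumed; no practice effect; the optional 50-54 stratum left out. Digital norm: A and C phase 1 plus E. Paper norm, assumed: B and D phase 1. TOST pass rates over r = .6-.8:

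| True shift | Separate norms, bound in norm SD | Separate norms, bound in SD of difference | One norm, either unit |
|---|---|---|---|
| 0 | 93-97% | 73-91% | 99-100% |
| .3 SD | same | same | 0-7% |
| 1 SD | same | same | 0% |
| 2 SD | same | same | 0% |

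With separate norms the rate stays below 100% because sampling error in the two norms adds variation that the paired standard error does not include. It is not a response to the shift.

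**5. What survives under separate norms.** In A the format difference is δ minus the paper practice effect. In B it is δ plus the digital practice effect. Averaged over equal groups it is δ + (digital practice − paper practice)/2. Norms from first administrations remove δ, so half of any practice difference remains. For assumed differences of .2, .3 and .5 SD that is .1, .15 and .25 SD. The pass rate at r = .7 with norm-SD bounds then falls to about 83%, 67% and 28%, give or take a few points depending on the overall practice effect assumed.

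**The case against.** The text does not adopt separate norms. The z-score definition refers to a norm sample in the singular, and Aim 3 defines one norm group. A reader who uses only the norms that the plan defines would place both formats on the digital norm, and the TOST then works. The word about computing scores separately may mean only that each participant gets one score per version. This stands, and it is why the point is conditional. But the reference to the Aim 3 procedure also permits a second regression on paper data, so the ambiguity is real. A published external paper norm is a third possibility; it would mix differences between norm populations into the result.

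Absorbing a raw shift may also be intended. Section 5 defines comparability on normed scores, section 3 says that the product reports norm-referenced scores, and claim 3 concerns similar psychometrics rather than interchangeable raw scores. This stands as a legitimate aim. On that aim, though, the mean TOST has little left to test and is not evidence of equal level.

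The between-subjects comparison is not restricted to normed scores, and on raw scores it would show a shift. True, but with no scale or criterion in section 7 it cannot fail a test.

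A reader might infer that the plan's test is blind to format shifts, or that a tablet version 1 or 2 SD harder will be declared comparable. The documents do not support that: it follows only under one reading, with a paper norm that the plan does not name. Nor do they support calling the power figures wrong, since those reproduce in one of the two possible units.

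**Conclusion.** The concern holds in conditional form. The norm for the paper score is unidentified under any reading, and that choice determines whether half of the comparability criterion can detect a constant format difference. The invariance under format-specific norms is exact. The pass-rate levels rest on the assumptions in the simulation: B and D phase 1 as the paper norm, r of .6-.8, a linear age effect and no practice effect. The test is not wholly inert even then, because half of a between-format difference in practice effects survives. No other analysis in section 7 has a criterion that would catch a level shift.

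Should-fix rather than must-fix: a one-norm reading is open and, if intended, a short clarification settles it. Left open, the choice could be made after the data are seen.

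**What to change.** 1. For the Hypothesis A mean TOST only, reference both formats to one norm named in advance: paper first administrations (B and D phase 1, n = 100 + 50 = 150), because paper is the comparator. This amounts to testing the raw digital-minus-paper difference divided by the paper age-residual SD, so the criterion can stay worded in normed scores. The norm must be fixed because the margin depends on it: if the digital SD were 1.5 times the paper SD, .3 digital SD would be .45 paper SD.
2. Keep format-specific norms for Aim 3.
3. State whether the .3 means norm SD or SD of the difference. With SD of the difference, the stated 99% and ±.21 stand. With norm SD, restate the power as about 99.8-100% at ±.3 and 91-99.8% at ±.21 (r .6-.8).
4. If only standing within each format's own norm is intended, say so and do not present the mean TOST as evidence of equal level.

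Cost: a protocol amendment with IRB approval and investigator signature (section 9) and changed analysis code; no new data. Tests with a real shift can now fail. Over r .5-.8, a true .1 SD shift passes 88-100% of the time with norm-SD bounds, or 64-88% with SD-of-difference bounds. A .2 SD shift passes 41-71% or 3-41% of the time. For example, at r = .5 and a .1 shift: Φ((.3 − .1) × 14.142 − 1.645) = Φ(1.183) = 88%.
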